6.5 STATISTICAL METHODS PLANNED IN THE PROTOCOL & DETERMINATION OF SAMPLE SIZE

6.5.1 STATISTICAL AND ANALYTICAL PLANS

6.5.1.1. Primary endpoint

To quantify if the biomarkers BRAF, IGF-1RP/MMP-7 (DP), DP and PIK3CA-PTEN improve the prediction of 12-months progression-free survival (PFS) over the use of just clinical variables in the study population we compared the area under the curve (AUC) of a ROC curve using scores composed by clinical variables with the AUC of scores with the clinical variables plus each of the biomarkers.

PFS was defined as the time from the signature of the ICF date to the radiological progression date or death (whatever occurs first). Subjects who had not shown PD and had not died at database closing were censored on the last date of radiological assessment. Subjects who had concluded study treatment before 48 weeks, due to any cause, underwent follow-up every 12 weeks as described in the protocol. Subjects who had undergone metastatic surgery were not censored on the surgery date but were followed up every 12 weeks until progression was documented. Subjects who received other treatment schemas maintaining the same strategy (chemotherapy + monoclonal antibody) without documented PD, were not censored at the time of the change of treatment. Progression to first line for these patients was considered when applicable according RECIST, independently of treatment received. If by any cause, the baseline CT scan was the only imaging evaluation performed (e.g., subject refusal to stay in the study or lost to follow-up), the case was censored on the inclusion date +1 day.

Two groups with a higher and lower likelihood for tumor progression until 12 months were determined based on the designated classification of clinical variables and following proposed biomarker categories :

1. wt-BRAF vs mutant BRAF

2. wtPI3K and PTEN >3 vs mutant PI3K or PTEN ≤3
3. Non-DP vs DP

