10.2.5 Considerations about the sample size

Two groups will be defined based on the classification constructed from the clinical variables and the proposed biomarkers.

The Log-rank method has been used instead of a binomial method for the sample calculation in order to include all the events that occur during follow-up.

A minimum difference of 20% (60 vs. 40%) in PFS is expected at 12 months between groups and with the following assumptions:

Alpha error (bilateral): 5%

Beta error: 20%

Monthly recruitment: 8 patients

Percentage of patients with classification = 0 is 40%

The number of patients required is 155 patients to be recruited in 24 months and a total duration of the trial (recruitment + follow-up) of 28 months for 115 events to occur.

Assuming 10% non-evaluable pts we should include a total of 170 pts.

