Statistical methods	
Sample size considerations
 
Initially, the number of patients required to be recruited in 24 months was 155 and the total study duration (recruitment + follow-up) was considered to be 28 months for 115 events to occur. After recruiting 157 patients, it was determined that about 70 of these patients had insufficient samples for biomarker analysis preventing their inclusion in the analysis of the primary objective. Therefore, in order to reach the 115 events necessary to evaluate the primary endpoint, the total number of patients to be included in the trial was increased up to 240. Finally, 221 patients were considered sufficient to observe the required number of events. After central reviewing and monitoring, 181 patients with wt-RAS were finally included for efficacy analysis.
 
For sample size calculation, it was assumed that patients could be classified into 2 groups based on their clinical characteristics and their biomarker profile. The log-rank method was planned to be used for the comparison of PFS during follow-up between the two groups. A minimum difference in PFS of 20% (50% vs 30%) was expected between the groups at 12 months, given the following assumptions:
 
 • Alpha error (two-tailed): 5% • Beta error: 20% 
Statistical considerations
 
The primary and the secondary efficacy objectives were analysed using per-protocol analysis. Patients fulfilling all eligibility criteria and with documented wt-RAS status (KRAS and NRAS) were included in the efficacy analysis.
 
Efficacy analysis was based on radiological imaging performed throughout the study and assessed by site investigators. Any finding considered as non-evaluable by the investigator was excluded from the analysis (it was considered as non-existent).
 
For continuous variables, mean, standard error (for efficacy variables), standard deviation (for other measurements), median, 25th percentile, 75th percentile, minimum and maximum, were considered. Categorical variables are presented using frequencies and percentages.
 
The 95% two-sided confidence intervals (CI 95%) of Kaplan–Meier

---------------------	---

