6.5.2. DETERMINATION OF SAMPLE SIZE

It was the aim of the study to identify two groups based on the well-established categories of clinical variables and the proposed biomarkers which are prognostic regarding PFS. The sample size should be sufficient detect a clinically relevant difference in PFS with a log-rank test between the two groups, given the following assumptions:

- The difference in PFS at 12 months between the two groups is at least 20% (i.e. 50% vs 30%) corresponding to a hazard ration of 1.79 assuming an exponential distribution. • Alpha error (two-tailed): 5%
- Beta error: 20%
- Monthly recruitment: 8 patients
- Percentage of patients with classification= 0: 40%

Initially, the number of patients required to be recruited in 24 months was 155 for 115 events to occur. Assuming a 10% proportion of potentially non-assessable patients, a total of 170 patients were needed to be included. After recruiting 157 patients, it was determined that about 70 of these patients had insufficient samples for biomarker analysis preventing their inclusion into the analysis of the primary objective. Therefore, in order to observe the 115 events necessary to evaluate the primary endpoint, the total number of patients was increased up to 221 recruited in 47 months (4–5 patients per month). Finally, the total study duration was 70 months (recruitment + follow-up).

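### The SAP's primary analysis compares 12-month AUCs, but the 115 events and 80% power were calculated for a log-rank test between two groups of a combined classification; the stated hazard ratio also does not match 50% vs 30%

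*SAP*

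**What the plan says.** **Analysis.** SAP 6.5.1.1 asks whether BRAF, DP and PI3K-PTEN improve prediction of 12-month PFS beyond clinical variables, and answers it by AUC: "we compared the area under the curve (AUC) of a ROC curve using scores composed by clinical variables" against scores with each biomarker added. SAP 6.5.1.5 gives the steps: Cox coefficients, a logistic model for 12-month PFS, a cut point, and comparison of four scores by ROC curves. The SAP Synopsis already reports AUCs of 0.67 (clinical), 0.68 (with BRAF, p = 0.37), 0.69 (with PI3K/PTEN, p = 0.32) and 0.66 (with DP, p = 0.09).

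**Sizing.** Protocol 10.2.5: "Two groups will be defined based on the classification constructed from the clinical variables and the proposed biomarkers", and "A minimum difference of 20% (60 vs. 40%) in PFS is expected at 12 months between groups". SAP 6.5.2: "The sample size should be sufficient detect a clinically relevant difference in PFS with a log-rank test between the two groups", with 50% vs 30% at 12 months, "corresponding to a hazard ration of 1.79 assuming an exponential distribution", and "Percentage of patients with classification= 0: 40" per cent. Both use two-sided 5% and beta 20%, and both arrive at 115 events. When enrolment was raised, the reason given in SAP 6.5.2 was "in order to observe the 115 events necessary to evaluate the primary endpoint".

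**The concern.** The test that was sized and the test called primary answer different questions. The first asks whether two groups, formed from clinical variables and markers together, differ in PFS. The second asks whether one marker adds discrimination at 12 months once the clinical variables are known. Power for the first does not transfer to the second.

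None of the three p-values in the Synopsis is below 0.05. Next to a statement that 115 events are what the primary endpoint needs, with beta 20%, a reader could conclude that the markers had an adequately powered test and failed. The plan gives no basis for that conclusion, and it bears on the primary objective.

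**Working it through.** **1. Reproducing 115 events.** Inputs from protocol 10.2.5: 60% vs 40% at 12 months, two-sided 5%, 80% power, 40% at classification 0. I assume classification 0 is the better group; the documents do not say.

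- HR = ln 0.40 / ln 0.60 = 1.794; k = 60/40 = 1.5.
- Freedman: d = (1.960 + 0.842)² (1 + k·HR)² / [k (HR − 1)²] = 7.849 × 13.62 / 0.945 = 113.1, so 114 events.
- Power at 115: Φ(√(115k)(HR − 1)/(1 + k·HR) − 1.960) = 81%.

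So 115 is, within rounding, an unequal-group log-rank number. It contains no AUC.

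**2. The hazard ratio.** For 50% vs 30%, ln 0.30 / ln 0.50 = 1.737. The SAP states 1.79, which belongs to 60% vs 40%.

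**3. Does 115 still serve 50% vs 30%?** At HR 1.737 with a 40/60 split:

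| Method | Events for 80% | Power at 115 |
|---|---|---|
| Freedman, 60% in worse group | 126 | 77% |
| Schoenfeld | 108 | 83% |
| Freedman, 40% in worse group | 101 | 85% |
| Simulated log-rank, 60% / 40% in worse group | – | 81% / 84% |

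**4. Which scenario produced the plan?** The accrual inputs point the other way from step 1. Take 155 patients at 8 per month (R = 155/8 = 19.4 months), T = 28 months and λ = −ln(12-month PFS)/12. The event probability is 1 − [exp(−λ(T − R)) − exp(−λT)]/(λR).

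- 50% vs 30%: 155 × (0.4 × 0.634 + 0.6 × 0.814) = 115.1 events.
- 60% vs 40%: 155 × (0.4 × 0.528 + 0.6 × 0.730) = 100.6 events.

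The event formula fits 60% vs 40%; the calendar fits 50% vs 30%. The documents do not settle which one was used.

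**5. Single markers, for scale only.** Group sizes are from SAP Table 6. The assumption that one marker carries the whole planned HR (1.737 to 1.794) is mine, not the plan's. Schoenfeld power is Φ(√(115·p(1 − p))·ln HR − 1.960). For BRAF p = 20/181, so √(115 × 0.0983) × 0.552 − 1.960 = −0.10, giving 46%. Freedman is as in step 1, with k = marker-positive/marker-negative and the positive group worse.

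| Marker | Split | Schoenfeld | Freedman |
|---|---|---|---|
| BRAF mutant | 20/181 | 46–50% | 63–69% |
| DP | 23/181 | 50–55% | 67–73% |
| PI3K mutant or PTEN ≤3 | 98/167 | 83–87% | 78–82% |

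Simulated log-rank power for BRAF was 52–57%, between the two formulas.

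**6. The AUC comparison.** Its power cannot be derived, because the plan states no AUC gain, no correlation between scores and no test. As an illustration, take a base AUC of 0.67, 181 patients, half with an event by 12 months, Hanley–McNeil variances and correlation 0.6 to 0.9. Power is then 8–20% for a gain of 0.02, 21–62% for 0.04 and 30–82% for 0.05. The AUC changes in the Synopsis are 0.68 − 0.67 = 0.01, 0.69 − 0.67 = 0.02 and 0.66 − 0.67 = −0.01.

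**The case against.** The SAP does not hide the log-rank basis. Its Synopsis says "The log-rank method was planned to be used for the comparison of PFS during follow-up between the two groups" and still lists PFS in two cohorts as the primary criterion. No passage claims power for the AUC comparison, and the conclusions field is blank. SAP 6.5.1.5 already places BRAF in a multivariable Cox model, and the Synopsis describes such analyses for BRAF and PI3K-PTEN. The last patient completed in 2017, so the size cannot change. All of this stands, and it keeps the remedy small. It does not remove the mismatch: 6.5.1.1 and 6.5.1.5 assign no log-rank test to the groups they form, and 6.5.2 still ties the 115 events to the primary endpoint.

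A reader might also infer more than the documents support:

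- *That 115 events are too few for 50% vs 30%.* The 126-event figure comes from one formula and one reading of which group holds the 40%; the other rows in step 3 give 81–85% power.
- *That BRAF or DP would need more events than the 181 patients analysed.* Schoenfeld gives 208–262 events, but Freedman gives 136–172.
- *That the AUC comparison is shown to be badly underpowered.* Step 6 runs from 8% to 82%.
- *That the power was planned for groups fixed in advance.* The formula treats membership as known, but protocol 10.2.5 and 10.4 build the classification from the trial data.
- *That the plan relies on an inflated log-rank test between the cut-point groups.* No such test is specified in 6.5.1.5.

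**Conclusion.** The point holds. The 115 events and 80% power belong to a two-group log-rank comparison. They support neither the AUC comparison that the SAP calls primary nor a test of any single marker, so the three AUC p-values are not negative results with 80% power. This rests on the text alone and needs no simulation.

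The hazard ratio of 1.79 in SAP 6.5.2 is wrong for 50% vs 30% (1.74). That is an error of labelling, not a demonstrated shortfall: 115 events give about 77–85% power at 50% vs 30%.

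The single-marker figures hold only under the assumed HR of 1.74 to 1.79 and exactly 115 events. BRAF and DP stay below 80% by either formula; PI3K/PTEN is near or above it.

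**What to change.** 1. In SAP 6.5.2, state that 115 events and 80% power refer only to the two-group log-rank comparison; that the calculation treats group membership as known although the plan builds the groups from the same data; and that no power was planned for the AUC comparison or for single markers. Reword the phrase that makes 115 events a requirement of the primary endpoint.
2. Give HR 1.74 for 50% vs 30%, or restore 60% vs 40%, and reconcile protocol 10.2.5 with SAP 6.5.2. Do not add a claim of shortfall.
3. Report each marker's added value by a 1-df likelihood-ratio test in the Cox PFS model with versus without the marker, in the same patients, with HR and 95% CI.
4. Report each AUC change as a paired difference with 95% CI in the same patients (167 for PI3K/PTEN), and state that a non-significant difference is not evidence against the marker.
5. If a log-rank test between the cut-point groups of 6.5.1.5 is reported, call it descriptive, because the coefficients and the cut point come from the same patients.

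Label items 3–5 post hoc, since AUC results already stand in the Synopsis. The cost is a less favourable power statement and a little extra analysis; no new data are needed.

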	
quartiles were calculated according to Brookmeyer and Crowley methods (55,56). Safety data were analysed throughout the entire study.
 
In the first step to develop a prediction model for PFS, univariate Cox regression analysis including all clinical variables collected in the study was performed in order to identify which should be considered for the model selection thereafter in the second step. All factors with a ≤ 0.15 p value (Appendix 15.2, item 4) were selected for the multivariable Cox analysis. The cut-off of ≤ 0.15 p-value was used in order to include the presence of resectable liver metastases as that is a well-known prognostic factor in mCRC. In the second step multivariable Cox regression analysis was performed including those variables identified in the univariate analysis. Importantly, the variable treatment (FOLFIRI vs FOLFOX) was not included for the development of the prediction score because it was not a characteristic intrinsic to the patients.

--	--

12-MONTHS PFS RISK MODEL DEFINITION

Clinical variables and biomarkers were used to build a score to predict 12-months PFS, by using a multivariable Cox regression model built with those clinical variables with a $p \leq 0.15$ in the multivariable analysis (performance status, chemotherapy regimen, sidedness, resectable only liver metastases). Once the first risk score was built adding up the coefficients of the multivariable model ($PS > 0 = 0.6$, left sided = -0.5, resectable liver only metastases = -0.4 and folfiri+cetuximab therapy = Not evaluable), ROC curves were computed for PFS at 12 months using a logistic regression model. All 4 scores (A. Clinical variables including PS, sidedness and resectable only liver metastases, B. Clinical variables + BRAF mutation; C. Clinical variables + PI3K mutation or PTEN ≤ 3 ; D. Clinical variables + DP) had comparable low areas under the curve, ranging between 0.5 and 0.7, overall: The AUC of the score containing the clinical variables was 0.67 (95% CI) (0.60-0.75).

The AUC of the score with clinical variables and BRAF mutational status was 0.68 (0.61-0.75, p-value = 0.37). The AUC of the score with clinical variables and PI3KCA mutation/PTEN status was 0.69 (0.61-0.76, p-value = 0.32). The AUC of the score with clinical variables and DP phenotype was 0.66 (0.58-0.73, p-value = 0.09).

SAFETY RESULTS

CONCLUSIONS

DATE OF THE REPORT:

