2. A score was established for each patient by adding up the regression coefficients of the multivariable Cox model present in these patients. If for example PS>0 was a negative predictor for PFS (i.e. regression coefficient is negative; e.g. -0.5) and left side tumour was a positive prognostic factor (regression coefficient was positive, e.g. 0.6) then for a patient with PS>0 and left sided tumour the two scores were added (-0.5 + 0.6=0.1). If a patients has PS=0 then the score to be added is 0, as it is the case for right sided tumour in the example.
3. Using a logistic regression model for the outcome 12-months PFS, a ROC curve was computed to choose the score cut point that classifies most patients correctly 4. Patients were dichotomized according to that cut point.
5. Steps 2 to 4 were repeated, adding each of the three biomarkers.
6. Definition of the discriminating power of the 4 scores for prognosis of or 12-months PFS according to these results were compared via ROC curves.
7. Determination of the most suitable score for 12-months PFS according to these results.

The four scores included in the first multivariate model using clinical factors where PS>0, chemotherapy with FOLFIRI and cetuximab, left sided and resectable liver metastases were considered (Score 1). The additional scores considered the four clinical factors above plus the status of each biomarkers (Score 2: BRAF mutation; Score 3: PI3K mutant or PTEN ≤ 3) and Score 4: Double-positive Phenotype (DP).

All analyses were performed using SAS V9.3 (SAS Institute, Cary, NC, USA) statistical software.

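### The primary comparison of ROC areas between nested, same-sample scores has low power to show that a marker adds anything, so its non-significant p-values cannot support a finding of no added value

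*SAP*

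**What the plan says.** SAP 6.5.1.1 (Primary endpoint) asks whether each of BRAF, DP and PI3K-PTEN improves prediction of 12-month PFS beyond clinical variables. It answers by ROC area: "we compared the area under the curve (AUC) of a ROC curve using scores composed by clinical variables with the AUC of scores" that contain the clinical variables plus one marker.

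SAP 6.5.1.5 gives the construction.
- Weights: "A score was established for each patient by adding up the regression coefficients of the multivariable Cox model present in these patients".
- Outcome and cut point: "Using a logistic regression model for the outcome 12-months PFS, a ROC curve was computed to choose the score cut point". Patients are then dichotomised at that cut point.
- Nesting: "Steps 2 to 4 were repeated, adding each of the three biomarkers".
- Comparison: "Definition of the discriminating power of the 4 scores for prognosis of or 12-months PFS according to these results were compared via ROC curves".

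The Synopsis gives clinical weights (PS>0 = 0.6, "left sided = -0.5, resectable liver only metastases = -0.4") and results. "The AUC of the score containing the clinical variables was 0.67 (95% CI) (0.60-0.75"); for BRAF, "The AUC of the score with clinical variables and BRAF mutational status was 0.68 (0.61-0.75, p-value = 0.37"). For PI3K-PTEN the area is 0.69 (p = 0.32) and for DP 0.66 (p = 0.09).

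Neither place names the test behind these p-values, says whether the continuous or the dichotomised score enters it, or mentions a split sample, cross-validation or bootstrap. The only stated alpha and power (5% two-sided, 80%) belong to the log-rank sizing in SAP 6.5.2.

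**The concern.** Paired tests of two ROC areas treat both scores as given in advance. Here the larger score is the smaller one plus a marker, and both sets of weights are estimated in the patients being tested. If the marker has no effect, its fitted weight is near zero, the two scores nearly coincide, and the usual normal reference distribution for the difference in areas does not apply. The area is also a blunt measure of added information: a marker can be clearly related to PFS and still move the area by only one or two hundredths. Finally, the comparison reduces PFS to a yes/no outcome at month 12, so event times enter only through the weights.

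What is at stake is how the primary result is read. With p-values of 0.37, 0.32 and 0.09, a reader would naturally conclude that the markers add nothing to the clinical variables. That conclusion is only as good as the test's chance of detecting a marker that does add something.

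**Working it through.** **Step 1. The plan's own sizing.** Under exponential PFS, HR = ln(S2)/ln(S1). The protocol's 60% vs 40% (section 10.2.5) gives ln 0.40/ln 0.60 = 1.794. Freedman's formula for unequal groups, events = (z_a + z_b)²(1 + k·HR)²/[k(1 - HR)²], with k = 0.6/0.4 = 1.5 and (1.960 + 0.842)² = 7.85, gives 7.85 × 13.62/0.946 = 113.1, or 114. This reproduces the stated 115 closely. It is a log-rank calculation for two composite groups; nothing in the plan sizes the AUC comparison.

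(The SAP pairs 1.79 with 50% vs 30%, but ln 0.30/ln 0.50 = 1.737. That is a separate discrepancy. I keep 1.79 as an illustration.)

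**Step 2. Simulation inputs.**
- From the SAP: the three clinical weights in the Synopsis; marker-positive counts from Table 6: BRAF 20 of 181, PI3K-PTEN 98 of 167 (69 + 98), DP 23 of 181.
- Assumed: DeLong's test; prevalences of PS>0 50%, left-sided 70%, resectable liver-only 15%; 12-month PFS 40% at the average risk; exponential PFS; censoring uniform over 12-60 months, none before month 12.

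Each simulated trial fits the clinical and the clinical-plus-marker Cox models in the same patients, compares the areas of the two linear predictors for progression by month 12, and also runs the Cox likelihood-ratio test (LRT). The average simulated clinical AUC is 0.666, against the SAP's 0.67.

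**Step 3. Results, continuous scores, nominal two-sided 5%.**

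| Marker | Size: AUC test | Size: Cox LRT | Power at HR 1.79: AUC test | Power: logistic LRT at month 12 | Power: Cox LRT |
|---|---|---|---|---|---|
| BRAF | 2.4% | 6.1% | 14% | 44% | 61% |
| PI3K-PTEN | 2.3% | 5.4% | 27% | 77% | 92% |
| DP | 2.4% | 5.2% | 15% | 48% | 69% |

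The logistic column uses the same binary 12-month outcome as the ROC analysis. For BRAF, replacing the AUC test by a likelihood-ratio test on that outcome gains 44 - 14 = 30 points; using all event times gains a further 61 - 44 = 17. Most of the loss therefore comes from testing through the area, not from stopping at month 12.

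Repeat runs with other seeds, and with follow-up of 23-70 months (47 months of accrual, 70 in total), gave AUC-test power of 13-16% for BRAF and DP and 24-28% for PI3K-PTEN, and Cox LRT power up to 70% and 94%.

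**Step 4. Sensitivity.**
- Other clinical prevalences (30/60/10% and 60/80/25%) and 12-month PFS of 35% or 50%, run for BRAF and PI3K-PTEN: AUC-test size 2.0-3.4%; power at HR 1.79 12-16% (BRAF) and 24-30% (PI3K-PTEN).
- About 107-116 events, close to the planned 115: AUC-test size 1.2-1.3%; AUC-test power 15% (BRAF), 23% (PI3K-PTEN), 14% (DP); Cox LRT 54%, 81%, 59%.
- Dichotomised scores, cut where most patients are classified correctly: size about 5-8%; power 12-26%.
- HR 2.5: AUC-test power 34%, 62%, 37%; Cox LRT 96%, above 99%, 98%.

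**Step 5. Disagreement within one trial.** At HR 1.79 the Cox LRT is significant while the AUC test is not in 50% (BRAF), 66% (PI3K-PTEN) and 55% (DP) of simulated trials.

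**The case against.** **The p-values are invalid.** A reader might infer this from the nesting and same-sample fitting. The documents do not support it as a general statement, because they fix neither the test nor the form of the score. With continuous scores and DeLong the test is conservative, and a conservative test still controls false positives. With dichotomised scores the size is near or somewhat above 5%. What holds in both forms is the low power.

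**The trial has 14-27% power where it planned 80%.** This too goes further than the text. The hazard ratio of 1.79 was set for two groups built from clinical variables and markers together, with 40% in one class. No document assumes it for a single marker, least of all one present in 11-13% of patients. It serves here only as a scale.

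**The SAP declares the markers useless.** It does not. The Conclusions heading is empty, no decision rule is attached to the AUC p-values, and section 6.5.1.1 speaks of quantifying an improvement. For DP the area fell from 0.67 to 0.66, so p = 0.09 does not hint at a missed gain in discrimination either. The objection stands as far as wording goes. But these are the p-values of the primary comparison, and they will be read as its answer.

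**Cox analyses are already there.** The Synopsis describes multivariable Cox analyses with BRAF and PI3K-PTEN, and section 6.5.1.5 lists BRAF among the variables chosen in advance. This helps but does not cure the problem: neither is designated the test of added value, and DP is not named in either place, although Score 4 implies a DP coefficient.

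**The likelihood-ratio test would find the markers.** Not reliably. At HR 1.79 it still misses about a third of BRAF or DP effects.

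**Conclusion.** The concern holds as a matter of power and specification. The primary comparison uses an unnamed test on an unspecified form of score. In either form it has about 12-28% power (up to 30% in the sensitivity runs) to detect a single-marker hazard ratio of 1.79 at the marker counts in Table 6. A Cox likelihood-ratio test in the same patients has about 61-70% for BRAF and DP and 92-94% for PI3K-PTEN with full follow-up. Non-significance in the AUC comparison is the likely outcome even for a marker of that strength, so p = 0.37 or 0.32 says little against BRAF or PI3K-PTEN.

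The figures rest on exponential PFS, assumed clinical prevalences, no censoring before month 12 and, for continuous scores, DeLong's test. The size statement depends on the form of the score: about 1-3% continuous, about 5-8% dichotomised. The ordering of the tests did not change in any setting tried. It is not established that any of the three markers does add predictive value; the point is that this analysis could not have ruled it out.

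**What to change.** 1. For each marker, make the inferential test the one-degree-of-freedom likelihood-ratio test of adding it to the clinical Cox model for PFS, using all events. Fit both models in the same patients, namely those with that marker measured. This matters for PI3K-PTEN, where Table 6 has 167 patients and not 181.
2. State a multiplicity rule for the three tests, for example Holm. Three independent tests at 5% have a familywise error of 1 - 0.95³ = 14.3%.
3. Keep the change in 12-month AUC as an estimate, with a bootstrap interval that repeats the whole fitting in each resample, and drop its p-value. State whether the score is continuous or dichotomised.
4. Label the change post hoc, since the AUC results are already in the Synopsis, and report the existing p-values beside the new test.

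Cost: SAP wording and a re-run on existing data; Cox regression for PFS is already specified. There are two real downsides. The test addresses association with PFS over all follow-up and not 12-month discrimination alone, a shift the sponsor must own. And multiplicity control costs power. In the worst case under Holm, a marker is tested at 0.05/3 (z = 2.394): BRAF goes from 61% to Φ(1.960 + 0.279 - 2.394) = 44%, DP from 69% to Φ(1.960 + 0.496 - 2.394) = 52%, and PI3K-PTEN from 92% to Φ(1.960 + 1.405 - 2.394) = 83%. Those bounds are still well above the AUC comparison without any adjustment.
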